**Other secondary efficacy endpoints:**

- Proportion of patients with EASI-50 at week 16
- Proportion of patients with EASI-90 at week 16
- Change from baseline to week 16 in percent BSA affected by AD
- Percent change from baseline to week 16 in SCORAD
- Change from baseline to week 16 in weekly average of daily worst scratch/itch NRS score
- Proportion of patients with improvement (reduction) of weekly average of daily worst itch score  $\geq 4$  from baseline at week 16
- Proportion of patients with improvement (reduction) of weekly average of daily worst itch score  $\geq 3$  from baseline to week 16
- Change from baseline to week 16 in skin pain NRS
- Change from baseline to week 16 in patient's sleep quality NRS
- Change from baseline to week 16 in caregiver's sleep quality NRS
- Change from baseline to week 16 in health-related quality of life, as measured by CDLQI score (patients  $\geq 4$  years of age)
- Change from baseline to week 16 in health-related quality of life, as measured by IDQOL score (patients  $< 4$  years of age)
- Change from baseline to week 16 in Dermatitis Family Index, DFI score
- Change from baseline to week 16 in POEM score
- Topical treatment for AD – proportion of TCS medication-free days from baseline to week 16
- Mean weekly dose of low potency TCS through week 16
- Mean of caregiver missed workdays (CMW) from baseline to week 16

**Secondary endpoints for safety:**

- Incidence of skin infection TEAEs (excluding herpetic infections) through week 16\*
- Incidence of SAEs through week 16

\*Adjudicated by study medical director.

**Additional secondary efficacy endpoints (that are not in protocol):**

- Mean weekly dose of medium or high potency TCS through week 16

**Skin Pain NRS**

Skin pain will be assessed by the parent/caregiver at time points during Part B according to [Appendix 3](#). Skin pain will be measured during Part B using a skin pain NRS that was developed and tested for the study-relevant age group. This is an 11-point scale (0 to 10) in which 0 indicates no pain while 10 indicates worst pain possible. The parents/caregivers will be asked to:

“Think about all the areas of your child's skin with eczema. Answer the question below based on what you observe and what your child tells you (if applicable).”

“How would you rate your child's skin pain at its worst in the past 24 hours?”

Clinical sites will check and remind the parent/caregiver to complete the scale according to the time points in [Appendix 3](#). Parents/caregivers will be instructed on using the scale to record their child's skin pain score at the screening visit. Parents/caregivers will complete the rating scale DAILY for the 14 days prior to the baseline visit, for the 7 days prior to the week 2 visit, for the 7 days prior to the week 4 visit, for the 7 days prior to the week 16 visit, and for the 7 days prior to the week 28 visit. Clinical sites will check parent/caregiver data collected using an e-diary for protocol compliance and remind parents/caregivers to complete their e-diary throughout the study. Higher score indicates worse condition.

The baseline Skin Pain NRS score is defined as the prorated average of the Skin Pain scores reported continuously for 7 days right before the baseline visit (i.e. study day -7 to day -1). For post-baseline Skin Pain NRS score, the weekly mean of daily Skin Pain score is calculated as the average of the available reported skin pain score within the week. For example, if there are 3 scores available in a week, the prorated average = (score1 + score2 + score3)/3.

### **Sleep Quality NRS**

A sleep diary will be completed by the parent/caregiver at time points during Part B according to [Appendix 3](#). The sleep diary includes 2 questions assessing the caregiver's sleep, and 6 questions assessing the child's sleep based on caregiver observation. Sleep diary items, either alone or in combination will serve as subjective measures of sleep quality, difficulty falling asleep, nighttime awakenings, and sleep duration. Sleep quality will be measured using an 11-point NRS (0 to 10) in which 0 indicates worst possible sleep while 10 indicates best possible sleep. The parents/caregivers will be instructed to complete the questions about the child's sleep upon awakening for the day as well as to complete the questions about their own sleep.

Clinical sites will check and remind the parent/caregiver to complete the diary according to the time points in [Appendix 3](#). Parents/caregivers will be instructed on using the diary to record their child's sleep quality score at the screening visit. Parents/caregivers will complete the diary DAILY for the 14 days prior to the baseline visit, for the 7 days prior to the week 1 visit, for the 7 days prior to the week 2 visit, for the 7 days prior to the week 4 visit, for the 7 days prior to the week 16 visit, and for the 7 days prior to the week 28 visit. Clinical sites will check parent/caregiver data collected using an e-diary for protocol compliance and remind parents/caregivers to complete their e-diary throughout the study. Higher score indicates better condition.

The baseline Sleep Quality NRS score is defined as the prorated average of the sleep quality NRS scores reported continuously for 7 days right before the baseline visit (i.e. study day -7 to day -1). For post-baseline Sleep quality NRS score, the weekly mean of daily sleep quality score is calculated as the average of the available reported daily sleep quality score within the week. For

example, if there are 3 scores available in a week, the prorated average = (score1 + score2 + score3)/3.

**Body Surface Area (BSA) Involvement of Atopic Dermatitis**

Body surface area affected by AD will be assessed for each section of the body (head, trunk, arms, and legs) and will be reported as a percentage of all major body sections combined. The possible highest score for each region is:

Age	Head	Torso	Lower Extremities	Upper Extremities	Genitals
6 months - <2 years	18%	36%	28%	18%	0%
2 - <3 years	17%	36%	29%	18%	0%
3 - <4 years	16%	36%	30%	18%	0%
4 - <5 years	15%	36%	31%	18%	0%
5 - < 6 years	14%	36%	32%	18%	0%

Total BSA will be the sum of all individual body areas. Patients will undergo this assessment at the scheduled and unscheduled clinic visits according to [Appendix 3](#).

**SCORing Atopic Dermatitis (SCORAD)**

The SCORAD is a validated tool used in clinical research and clinical practice that was developed to standardize the evaluation of the extent and severity of AD (Dermatology 1993). The extent of AD is assessed by the Investigator as a percentage of each defined body area and reported as the sum of all areas, with a maximum score of 100% (assigned as “A” in the overall SCORAD calculation). The severity of 6 specific symptoms (erythema, oedema / papulation, excoriations, lichenification, oozing / crusts and dryness) of AD is assessed by the Investigator using the following scale: none (0), mild (1), moderate (2), or severe (3) (for a maximum of 18 total points, assigned as “B” in the overall SCORAD calculation). Subjective assessment of itch and sleeplessness is recorded for each symptom by the patient or relative on a visual analogue scale (VAS), where 0 is no itch (or sleeplessness) and 10 is the worst imaginable itch (or sleeplessness), with a maximum possible score of 20. This parameter is assigned as “C” in the overall SCORAD calculation. The SCORAD is calculated as  $A/5 + 7B/2 + C$ . The maximum SCORAD score is 103. The objective SCORAD is calculated as  $A/5 + 7B/2$ . The maximum objective SCORAD score is 83. Higher score indicates worse condition.

Patients will undergo this assessment at the scheduled and unscheduled clinic visits according to [Appendix 3](#).

### **Children’s Dermatology Life Quality Index (CDLQI)**

The CDLQI is a validated questionnaire designed to measure the impact of skin disease on the QOL in children  $\geq 4$  years of age (Lewis-Jones 1995). The aim of the questionnaire is to measure how much a patient’s skin problem has affected the patient over a recall period of the past week. In this study, a cartoon version of the CDLQI will be administered to patients 4 to 5 years of age, with the assistance of a parent or adult “as necessary”. If assistance of parent or adult caregiver is required, it is recommended that the same person assist the patient throughout the study. The cartoon version of the CDLQI uses the same text and scoring system as the original CDLQI but includes 10 color drawings of a dog illustrating the theme of each question.

To complete the questionnaire, patients need to provide responses to 10 questions (the questions focus on domains such as symptoms feelings associated with disease, the impact of the disease on leisure, school or holidays, personal relationships, sleep, and side effects of treatment for the skin disease. The instrument has a recall period of 7 days. Nine of the 10 questions are scored as follows:

- Very much = 3
- Quite a lot = 2
- Only a little = 1
- Not at all = 0
- Question unanswered = 0

Question 7 has an additional possible response (prevented school), which is assigned a score of 3. Overall scoring ranges from 0 to 30; a high score is indicative of a poor QOL. The CDLQI will be assessed at the scheduled and unscheduled clinic visits according to [Appendix 3](#).

Handling missing items from CDLQI:

- i. If one question is left unanswered this is scored 0 and the scores are summed and expressed as usual out of a maximum of 30.
- ii. If two or more questions are left unanswered the questionnaire is not scored.
- iii. If two or more response options are ticked for one question, the response option with the highest score should be recorded.
- iv. The CDLQI sub-scores may be analyzed by calculating the score for each of its six sub-scales. When using sub-scales, if the answer to one question in a sub-scale is missing, that sub-scale will not be scored:

Sub-scales	Questions	Maximum Score
Symptoms and feelings	Questions 1,2	6
Leisure	Questions 4, 5 and 6	9
School or holidays	Question 7	3
Personal relationships	Questions 3 and 8	6
Sleep	Question 9	3
Treatment	Question 10	3

### **Infants' Dermatology Quality of Life Index (IDQOL)**

The IDQOL is a validated questionnaire developed to measure the impact of skin disease on the QOL of infants and preschool children <4 years of age (Lewis-Jones 2001). The IDQOL is to be completed by the child's parent or caregiver. It is recommended that the same person complete the questionnaire on behalf of the patient throughout the study. The questionnaire consists of 10 questions related to itching and scratching; mood of the child; how long it takes for the child to get to sleep; whether the eczema has interfered with the child's playing, swimming or participation in other family activities; problems during mealtimes; problems caused by treatment; level of comfort while dressing or undressing the child; and problems during bathing. Each question asks about the impact over the previous week and is scored on a scale of 0 (minimum impact) to 3 (maximum impact). A high score is indicative of a poor QOL

The IDQOL for a patient is the sum of the score of each question with a maximum of 30 and a minimum of 0. The higher the score, the greater the impact is on the QOL. The IDQOL can also be expressed as a percentage of the maximum possible score of 30. Handling missing items from IDQOL will be same as that of CDLQI. The IDQOL sub-scores may be analyzed by calculating the score for each of its sub-scales, as appropriate. When using sub-scales, if the answer to one question in a sub-scale is missing, that sub-scale will not be scored.

This assessment will be performed in Part B at time points according to [Appendix 3](#).

Sub-scales	Questions	Maximum Score
Symptoms (1 item)	Question 1	3
Difficulties with mood (1 item)	Question 2	3
Sleep (2 items)	Questions 3, 4	6
Play (1 item)	Question 5	3
Family activities (1 item)	Question 6	3

Mealtimes (1 item)	Question 7	3
Treatments (1 item)	Question 8	3
Dressing (1 item)	Question 9	3
Bathing (1 item)	Question 10	3

**Patient Oriented Eczema Measure (POEM)**

The POEM is a 7-item, validated questionnaire used in clinical practice and clinical trials to assess disease symptoms in children and adults with atopic eczema (Charman 2004). The format is patient response to 7 items (dryness, itching, flaking, cracking, sleep loss, bleeding, and weeping) based on symptom frequency during the past week (i.e., 0 = ‘no days’, 1 = ‘1 to 2 days’, 2 = ‘3 to 4 days’, 3 = ‘5 to 6’ days, and 4 = ‘every day’). The total score is the sum of the 7 items which is ranged from 0 to 28; a high score is indicative of a poor QOL. The following POEM banding scores have been established (Charman 2004): 0 to 2 = Clear or almost clear; 3 to 7 = Mild eczema; 8 to 16 = Moderate eczema; 17 to 24 = Severe eczema; 25 to 28 = Very severe eczema. If two or more response options are selected for a question, then the response option with the highest score is recorded. If one question of the seven is left unanswered, then that question is scored as 0 and the scores are summed and expressed as usual out of a maximum of 28. If two or more questions are left unanswered, then the questionnaire is not scored and is set to missing. If two or more response options are ticked for one question, the response option with the highest score should be recorded. Higher score indicates worse condition.

This questionnaire asks the caregiver to report their perception of the patient’s AD symptoms. It is therefore completed by the caregiver. It is recommended that the same person complete the questionnaire on behalf of the patient throughout the study.

**Caregiver Assessment of Missed Workdays (CMW)**

Caregivers who are employed will be asked to report the number of sick-leave days since the last study assessment. Caregivers will undergo this assessment at the time points according to Appendix 3.

**Dermatitis Family Index (DFI)**

The impact on family life has been documented in families of children with very severe AD. The DFI was the first instrument assessing the impact of having a child with AD on family QOL (Lawson 1998). The 10-item disease specific questionnaire was formed after ethnographical interviews and focus groups revealed the areas of family QOL affected by AD. The self-administered instrument is completed by an adult family member of a child affected by dermatitis. The items inquire about housework, food preparation, sleep, family leisure activity, shopping, expenditure, tiredness, emotional distress, relationships and the impact of helping with treatment on the primary caregiver’s life. The DFI questions are scored on a four-point Likert scale ranging from 0 to 3, so that the total DFI score, which is calculated as sum of all 10 questions,

ranges from 0 to 30. The time frame of reference is the past week. A higher DFI score indicates greater impairment in family QOL as affected by AD. The DFI will be assessed at time points according to [Appendix 3](#). Note that, DFI is also called as Dermatitis Family Impact.

Handling missing items from DFI:

- v. If one question is left unanswered this is scored 0 and the scores are summed and expressed as usual out of a maximum of 30.
- vi. If two or more questions are left unanswered the questionnaire is not scored.
- vii. If two or more response options are ticked for one question, the response option with the highest score should be recorded.

#### 4.4.3. Exploratory Efficacy Variable(s)

Exploratory efficacy endpoints include:

- Proportion of patients with SCORAD-50 ( $\geq 50\%$  reduction in SCORAD from baseline) response at week 16
- Proportion of patients with SCORAD-75 ( $\geq 75\%$  reduction in SCORAD from baseline) response at week 16
- Proportion of patients with SCORAD-90 ( $\geq 90\%$  reduction in SCORAD from baseline) response at week 16
- Caregiver global impression of disease (CGID):
  - Proportion of patients with No symptoms at week 16
  - Proportion of patients with No symptoms or Mild symptoms at week 16
- Caregiver global impression of change (CGIC):
  - Proportion of patients who rate their eczema symptoms as “Much better” at week 16
  - Proportion of patients who rate “Much better” or “Moderately better” at week 16
- Proportion of patients who achieve reduction of IGA score by  $\geq 2$  from baseline to week 16
- Proportion of patients who achieve an IGA score of 2 (mild disease) or less at week 16
- Change from baseline to week 16 in GISS (erythema, infiltration/papulation, excoriations, lichenification)
- Proportion of patients with IGA score 0 or 1 or EASI-90 at week 16
- Change from baseline in PASQ score at week 16 (for patients with Asthma)
- Change from baseline in CNSQ score at week 16 (for patients with medical history of allergic rhinitis)

### **Caregiver Global Impression of Disease (CGID)**

The CGID is an assessment instrument used by the parent/caregiver in clinical studies to rate their child's eczema symptoms during the past 7 days. An appropriate version of the CGID was being developed and tested for the study-relevant age group.

Parents/caregivers will rate their child's disease based on the 5-level scale as follows:

“Overall, how would you rate your child's eczema symptoms during the past 7 days?”

- No symptoms
- Mild
- Moderate
- Severe
- Very severe

The CGID score will be assessed at time points according to [Appendix 3](#).

### **Caregiver Global Impression of Change (CGIC)**

Caregiver global impression of change will be measured using a caregiver administered tool that is currently being developed and tested for the study-relevant age group.

Parents/caregivers will respond to the following question based on the 7-level scale as follows:

“Compared to before your child started the study, how would you rate his or her eczema now?”

- Much better
- Moderately better
- A little better
- No change
- A little worse
- Moderately worse
- Much worse

The CGIC is an instrument used by the parent/caregiver in clinical studies to compare their child's eczema symptoms from the beginning of the study to when they completed the assessment.

The CGIC score will be assessed at time points according to [Appendix 3](#).

### **Global Individual Signs Score (GISS)**

Individual components of the AD lesions (erythema, infiltration/papulation, excoriations, and lichenification) will be rated globally by the Investigator (i.e., each assessed for the whole body, not by anatomical region) on a 4-point scale (0=none, 1=mild, 2=moderate and 3=severe) using the EASI severity grading criteria. The cumulative score is the sum of the four components, which

will be ranged from 0 to 12. A higher GISS score indicates worse AD lesions of the patient. Handling missing items from GISS:

- i. If one question is left unanswered this is scored 0 and the scores are summed and expressed as usual out of a maximum of 12.
- ii. If two or more questions are left unanswered the questionnaire is not scored.
- iii. If two or more response options are ticked for one question, the response option with the highest score should be recorded.

The GISS will be assessed at the scheduled and unscheduled clinic visits according to [Appendix 3](#).

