### **Pediatric Asthma Symptom Questionnaire (PASQ)**

The PASQ is a questionnaire developed by the sponsor to monitor asthma control in preschool children in clinical trial settings. The advantage of the PASQ is the much shorter recall period for various items to fit the schedule of clinical trials and improvement in ability to recall as compared to existing instruments. The questionnaire consists of 6 questions related to asthma control.

The questionnaire will be completed only for the subset of patients with ongoing asthma. It is to be completed by the child's parent or caregiver who fluently speaks a language in which the questionnaire is presented, at time points according to [Appendix 3](#). It is recommended that the same person complete the questionnaire on behalf of the patient throughout the study. Questions 4, 5, and 6 will only be answered if the answer to Question 3 is > 0 days. Higher score indicates worse condition (asthma severity).

The following algorithm will be implemented to calculate PASQ score.

- Questions 1 & 2 should still be calculated and summarized separately.
- For questions 3 to 6 (ranged from 0 to 4), total score, which can be termed as PASQ score. will be calculated.
  - If answer to question 3 is 0, then the total score is 0, regardless of answers to questions 4-6;
  - If answer to question 3 is non-zero and answers to questions 4 to 6 are all 0, then the total score will be equal to the score for question 3;
  - If answer to question 3 is non-zero and answers to questions 4 to 6 are also non-zero values, then the total score is calculated by adding the scores for questions 4 to 6; Also ignore the score in question 3.

Handling missing items from PASQ:

If answer to question 3 is missing and answers to questions 4-6 are non-missing, then the total score is calculated by adding the scores for questions 4 to 6; if one item from questions 4 to 6 is missing, set the score of the missing item as the average of the other two non-missing items from questions 4-6 and calculate total score. If two or more items from questions 4-6 are missing, then set the total score as missing.

If answer to question 3 is non-missing and non-zero, and if one item from questions 4-6 is missing, set the score for the missing item as the average of the other two non-missing items from questions 4-6 and calculate total score. If two or more items from questions 4-6 are missing, then set the total score as missing.

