### **Caregiver-Reported Nasal Symptom Questionnaire (CNSQ):**

The CNSQ will be used to assess the effect of study drug on symptoms of allergic rhinitis. The summed score will include the following 4 symptoms: runny nose, nasal congestion, nasal itching, and sneezing, each rated on a 0 to 3 scale of severity. The questionnaire will be completed only for the subset of patients with a medical history of allergic rhinitis. It is to be completed by the child's parent or caregiver who fluently speaks a language in which the questionnaire is presented (based on availability of translations in participating countries). Total score is the sum of all symptom scores. If there is one symptom score missing, the total score is set to missing. The minimum and maximum possible values of the total CNSQ score are 0 and 12. Higher score indicates worse condition.

Caregivers will be instructed on using the e-diary to record the CNSQ during the screening period (for the 14 days before baseline/day 1) and for the 7 days preceding visits for weeks 4, 16, and 28 as described in [Appendix 3](#).

The baseline CNSQ score is defined as the average of the CNSQ scores reported continuously for 7 days right before the baseline visit (i.e. study day -7 to day -1). The weekly average CNSQ score (post-baseline) will be calculated as the average of the available reported daily CNSQ score within 7 days prior to the visit. For example, if there are 3 scores available in a week, the average = (score1 + score2 + score3)/3.

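### A single unrecorded GISS sign is scored 0, the code for an absent sign, so an incomplete total enters an exploratory analysis as if it were fully observed

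*SAP*

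**What the plan says.** SAP 4.4.3 describes four signs (erythema, infiltration/papulation, excoriations, lichenification) that "will be rated globally by the Investigator", each "on a 4-point scale (0=none, 1=mild, 2=moderate and 3=severe"). The sum "will be ranged from 0 to 12", and "A higher GISS score indicates worse AD lesions of the patient".

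The item rules follow. The first, rule (i), reads: "If one question is left unanswered this is scored 0 and the scores are summed and expressed as usual", with 12 kept as the maximum. Rule (ii) leaves the total unscored when two or more signs are blank. The protocol's GISS section (6.2.2.14) has no rule for a missing sign.

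Change from baseline to week 16 in GISS is listed among the exploratory endpoints (SAP 4.4.3). Appendix 2 assigns it ANCOVA with the MI-WOCF pattern-mixture imputation of SAP 5.6.2 and lists no sensitivity analysis. GISS does not appear in the testing hierarchy of SAP 5.6.3.

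For the CNSQ, another sum of four items scored 0 to 3 with a total of 0 to 12, the same SAP section says: "If there is one symptom score missing, the total score is set to missing".

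**The concern.** On this scale 0 is a clinical finding: the sign is absent. Rule (i) therefore turns a gap in the record into the best possible rating for that sign. Because the total then looks complete, neither the multiple-imputation part nor the WOCF part of the planned method treats it as missing. SAP 5.6.2 also builds the imputation model on measured values at every clinic visit, so a total that is falsely low at an intermediate visit feeds into other patients' imputed values.

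At baseline the forced value can contradict the trial's own eligibility data. Part B requires IGA of at least 3 at baseline (protocol 4.2.1, criterion 4). Protocol Appendix 3 defines IGA 3 by moderate, and IGA 4 by severe, erythema and papulation/infiltration. A blank in either of those two GISS signs would be coded as absent in a child who qualified because both were at least moderate.

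What is at stake is the accuracy of a change score for an exploratory investigator-rated endpoint.

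**Working it through.** **Inputs.** Four signs, each 0 to 3, higher is worse, rule (i), and the endpoint as absolute change from baseline: SAP 4.4.3. Share of assessments with exactly one blank sign: not in the documents, assumed 1% to 10%. Mean true value of the missing sign: assumed 1 to 3.

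**1. The plan's own figure.** 4 × 3 = 12, which matches the stated range. With one sign forced to 0 the highest attainable total is 3 × 3 = 9, still expressed out of 12.

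**2. Error in one patient.** Let *x* be the true value of the unrecorded sign.

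- Recorded total = true total − *x*, with *x* between 0 and 3.
- Blank at week 16: recorded change = true change − *x*.
- Blank at baseline: recorded change = true change + *x*.

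With baseline signs 3, 3, 3, 3 (total 12):

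| True week 16 signs | True change | One sign blank at week 16 | One sign blank at baseline |
|---|---|---|---|
| 3, 3, 3, 3 | 0 | −3 | +3 |
| 2, 2, 2, 2 | −4 | −6 | −1 |
| 1, 1, 1, 1 | −8 | −9 | −5 |

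The error can be nil. If the true week 16 signs are 2, 2, 2, 0 and the last is the blank one, the true change is 6 − 12 = −6 and the rule also gives −6.

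**3. Baseline conflict.** If the GISS ratings agree with the IGA definitions, erythema and infiltration/papulation are each 2 at IGA 3 and 3 at IGA 4. A blank in either then lowers the baseline total by 2 or 3 points. Excoriations and lichenification are not part of the IGA definition and may truly be 0.

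**4. Shift in one arm's week 16 mean.** Shift = −*m* × *s*, where *m* is the share with one blank sign and *s* its mean true value.

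- Smallest: −0.01 × 1 = −0.01 points.
- Largest: −0.10 × 3 = −0.30 points.

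**5. Shift in the dupilumab minus placebo difference** (negative favours dupilumab). Shift = −*m*(dup) × *s*(dup) + *m*(pbo) × *s*(pbo). Taking *s* = 1 on dupilumab and 2 on placebo, as an assumption:

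- 2% blank in both arms: −0.02 + 0.04 = +0.02
- 10% blank in both arms: −0.10 + 0.20 = +0.10
- 10% on dupilumab only: −0.10
- 10% on placebo only: +0.20

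These are blanks at week 16. Blanks at baseline act with the opposite sign.

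**The case against.** **Scoring one blank as 0 is the SAP's usual convention.** CDLQI, IDQOL, POEM and DFI all use it, and they stand in the testing hierarchy (POEM 10th, DFI 14th, CDLQI 15th, IDQOL 16th), whereas GISS does not. This is correct. But those are forms completed by the patient or a family member. GISS is a clinical rating, and its rule repeats the questionnaire wording.

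**CNSQ is only a partial precedent.** It is a daily diary score averaged over the available days, so losing one day's total costs little; GISS is a single clinic rating. This stands as far as it goes: CNSQ shows that the SAP already has a suitable rule for a score of the same structure, not that the GISS rule contradicts it. PASQ is not a usable second precedent, because its total is gated on one question and normally sums three items.

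**The event should be rare.** Data are captured electronically, validated, checked against source and signed by the investigator (protocol 10.1, 11.1, 11.3). This is fair, although no frequency is stated.

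**The missing sign may truly be absent.** Protocol 1.1 describes papules and vesicles in infants and lichenified lesions from about 2 years of age. For an infant with unrecorded lichenification, 0 could be right. This stands: the error is 0 to 3 points, not always positive. It also counts against filling the gap with the mean of the other three signs.

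**A reader might infer that the rule favours dupilumab, or that it disables MI-WOCF for GISS.** The documents support neither. The rule is the same in both arms, and under the assumptions above equal missingness moves the contrast towards no effect. A shift towards dupilumab from week 16 blanks needs more missingness in that arm, for which there is no evidence. Totals with two or more blank signs and missed visits still go to the planned method, and data after rescue are replaced by WOCF in any case.

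**Conclusion.** The point holds as a minor flaw. When exactly one GISS sign is unrecorded, the SAP records it as absent and treats the total as observed. The affected total is too low by the sign's true value, 0 to 3 points out of 12. Improvement is overstated if the blank is at week 16 and understated if it is at baseline, where the forced 0 can also conflict with the IGA entry criterion. Rule (ii), for two or more blanks, is sound.

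The arm-level range of 0.01 to 0.30 points rests on the assumed 1% to 10% frequency and mean sign values of 1 to 3; the true frequency is probably small. The direction of any between-arm bias is not established. No primary, secondary or alpha-controlled result is affected.

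**What to change.** Replace rule (i) in the GISS section of SAP 4.4.3: if any of the four signs is missing at a visit, the total for that visit is set to missing and handled by the MI-WOCF method of SAP 5.6.2. This is the CNSQ rule, and it would absorb rule (ii).

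For a blank at baseline, the SAP's baseline definition (6.1, the latest valid value before the first dose) would then point to the screening total, since GISS is also scheduled at screening. It is worth saying so in the same line.

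The cost is one SAP line. The downside is that a few totals are imputed instead of computed, and three recorded signs at those visits no longer enter the total directly.
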